11.2.7 Esophago-Gastro-Duodenoscopy

An EGD will be performed during the screening period and again on Day 169 (± 3 days). During the EGD, endoscopic severity will be graded per the EoE Reference Score for Endoscopic Abnormalities and biopsies will be collected. Results from the Day 169 EGD biopsies will not be provided to the Investigator and/or Sponsor until after final database lock and unblinding. The Safety Monitor will review the EGD results and escalate any issues to the Medical Monitor and the Investigator, as appropriate, while maintaining the blind.

11.2.7.1 Eosinophilic Esophagitis Reference Score for Endoscopic Abnormalities

During the conduct of the EGD at screening and on Day 169 (or ET), the attending physician will assess and grade edema, rings, exudates, furrows, and strictures per the EREFS. The EREFS and the EREFS Scoring Tool source can be found in the study histology manual.

11.2.7.2 EGD Biopsy Collection

During the conduct of the EGD at screening and on Day 169 (or ET), a biopsy sample will be collected according to standardized instructions in the study histology manual and will be sent to the central histology lab for fixing and staining.

A blinded central reader will assess and report the maximum number of eosinophils/hpf,

CCI

CCI
CCI
(Appendix 9).

The Screening EGD biopsy tissue results must be available to verify eligibility per the following.

- Inclusion Criterion #2: Confirmed diagnosis of EoE and intraepithelial eosinophilic infiltration of ≥ 15 eosinophils/hpf in 1 hpf from the biopsy collected during the Screening EGD without any other cause for the esophageal eosinophilia.
- Exclusion Criterion #1: Concomitant moderately or severely symptomatic EG and/or EoD*, defined as:
 - ≥ 30 eosinophils/hpf in 5 hpf in the stomach (EG) and/or ≥ 30 eosinophils/hpf in 3 hpf in the duodenum (EoD) without any other cause for eosinophilia as determined by central histology assessment of biopsies collected during the Screening EGD.

and

- EG/EoD PRO Questionnaire weekly average single symptom score of ≥ 3 during the last 2 weeks of screening for 1 of the following symptoms: abdominal pain, nausea, and/or diarrhea.
- * This exclusion criterion is only applicable to sites actively enrolling subjects in the AK002-016 study. If a site is *not* actively screening and enrolling subjects in the AK002-016 study, then this exclusion criterion is not applicable.
- Exclusion Criterion #7: Active *Helicobacter pylori*** infection as determined by central histology staining of the biopsy collected during the Screening EGD.
 - ** If an active *H. pylori* infection at screening is treated with standard of care therapies, the subject's symptoms remain stable, and the subject is then confirmed negative for *H. pylori*, the subject may be randomized into the study.

11.2.8 Complete Blood Count with Differential

Blood for CBC with differential will be obtained at all study visits. On dosing days (Days 1, 29, 57, 85, 113, and 141), blood for CBC with differential will be drawn twice: predose and 1 hour postdose.

The blood sample will be processed and shipped in accordance with the central laboratory manual and lab kit instructions. The central laboratory will analyze the blood sample and provide results for CBC with differential, including hemoglobin, hematocrit, platelet count, red blood cell count, white blood cell count, and absolute differential count (neutrophils, lymphocytes, monocytes, eosinophils, and basophils).

As described in the Investigator's Brochure, expected effects of AK002 include changes in absolute lymphocyte and eosinophil counts, so these results could potentially unblind the blinded members of the study. Consequently, with the exception of screening and Day 1 predose, the CBC differential results (neutrophils, lymphocytes, monocytes, eosinophils, and basophils) will be blinded to both the Sponsor and the study site. The CBC differential results for Day 1 (1 hour postdose), Days 8, 15, 29, 57, 85, 113, 141, 169, and 197 (or ET) will therefore be unavailable during the study and will not be provided to the Sponsor or study site until after final database lock and unblinding.

The Safety Monitor will have real-time access to these laboratory results and will review and escalate any concerns/issues to the Medical Monitor and/or the site as appropriate. An unscheduled CBC, with differential may be collected if requested by the Safety Monitor. All panic alerts for blinded values will be sent to the Safety Monitor and evaluated in real time.

If the CBC differential results from Day 197 (or ET) show that absolute lymphocyte and/or eosinophil counts have not recovered (to normal range or baseline levels), the subject must return for Extended Follow-Up visits approximately every 28 days to monitor blood counts until lymphocyte and/or eosinophil counts have recovered. Extended Follow-Up visits will consist only of blood collection for CBC with differential and collection of any AESI and SAE.

11.2.9 Baseline Diet Assessment

During the screening visit, the Investigator or designee will interview the subject and perform a Baseline Diet Assessment using the series of standardized dietary assessment questions found in [Appendix 7](#). The Baseline Diet Assessment includes questions regarding eating patterns, food avoidance behaviors, and allergies, and will serve to establish the "Baseline Diet." Answers will be documented in the subject source documents and recorded in the eCRF.

If the subject is on diet therapy, the diet therapy and length of time on the current diet therapy will be documented during the Baseline Diet Assessment. Per Exclusion Criterion #11, the subject is ineligible if any changes were made to the diet therapy during the 8 weeks prior to screening. Additionally, if the Baseline Diet Assessment reveals preexisting dietary restrictions, the subject must be willing to maintain the same dietary restrictions ("Baseline Diet") for the entire duration of study participation per Inclusion Criterion #7.

11.2.10 Baseline Diet Compliance

Per Inclusion Criteria #7, the Baseline Diet (as defined and documented during the Baseline Diet Assessment) should be adhered to and maintained as much as possible for the entire duration of study participation, even if the subject feels the dietary restrictions are no longer necessary.

Compliance with the Baseline Diet will be discussed and assessed during study visits on Days 1, 15, 29, 57, 85, 113, 141, 169, and 197 (or ET). The Investigator or designee will document whether the subject was compliant with the Baseline Diet and, if not, all variances or deviations from the Baseline Diet will be documented in the source documents and eCRF.

11.3 Safety-Related Procedures

11.3.1 Concomitant Medications

All prior and concomitant medication and concurrent therapies will be documented at screening and assessed at all study visits. Concomitant medications, dose, route, unit, frequency of administration, indication for administration, dates of medication, and all changes will be captured. All prior medications (within 30 days before screening) and concomitant medications (during study participation from screening through Day 197 or ET) will be recorded.

For subjects participating in the OLE period, concomitant medications should be recorded in the AK002-014 treatment period database up until the first open-label dose is administered during the Day 176 visit. This includes the prednisone premedication administered prior to the Day 176 visit in the OLE period, which should be recorded in the Concomitant Medications CRF of both the AK002-014 treatment period database and the AK002-014 OLE period database. Rescue medications and procedures must be documented as rescue treatment in the source documents and on the prior and concomitant medications eCRF.

11.3.2 Stool Sample for Ova and Parasite

During the screening visit, subjects will be provided fecal collection kits for the Ova and Parasite (O&P) test. Subjects will take the kit home to collect a stool sample. Subjects must return the stool sample to the site on the day of collection (or within 24 hours of collection). The site will process and ship the stool sample per the central laboratory manual. The central laboratory will test the stool sample for O&P. Per Exclusion Criterion #8, a positive O&P result would make the subject ineligible, and a negative O&P result is required to confirm eligibility. Alternatively, a negative result from a helminth test done within 90 days prior to screening may be used to confirm eligibility, at the discretion of the Investigator.

11.3.3 Body Weight and Height

Height (in centimeters) and body weight (in kilograms) will be measured at screening and body mass index (BMI) will be calculated. Body weight must be measured prior to each dose of study drug (predose on Days 1, 29, 57, 85, 113, and 141). Predose weight should be measured at the site on the day before the study drug infusion or on the day of the study drug infusion, entered into the IRT system, and recorded on the IP Dose Calculation and Preparation Worksheet maintained by the study pharmacist for each subject's dose calculations.

Body weight will also be measured at the end of the treatment period (on Day 169) and at the end of study (Day 197 or ET).

11.3.4 Vital Signs

Vital signs including systolic and diastolic blood pressure, pulse, body temperature, and respiratory rate will be taken after the subject has been at rest for ≥ 5 minutes and, if possible, before any blood draw.

Vital signs will be measured during screening and on Days 1, 15, 29, 57, 85, 113, 141, 169, and 197 (or ET). On dosing days (Days 1, 29, 57, 85, 113, and 141), vital signs will be measured predose, 15 minutes (± 5 minutes) after the infusion start time, immediately postdose (within 5 minutes after the infusion end time), and 1 hour (± 5 minutes) postdose. Please refer to the schedule in [Table 1](#).

11.3.5 Complete Physical Examination

A complete physical exam will be performed during the screening visit by the Investigator or qualified Subinvestigator. A complete physical exam will include the following body system or organ assessments: skin; head, eyes, ears, nose, and throat; thyroid; lungs; cardiovascular; abdomen; extremities; lymph nodes; and a brief neurological examination.

The Investigator or qualified Subinvestigator will examine abnormalities and assess whether they are clinically significant or not clinically significant. All clinically significant abnormalities noted during the complete physical exam should be captured as a baseline condition in the Medical History source document and eCRF.

11.3.6 Symptom-Directed Physical Examination

If a new or worsening symptom (or clinically significant finding) is observed or reported, the Investigator (or qualified Subinvestigator) will perform a symptom-directed physical exam. The symptom-directed physical exam will focus only on body systems and/or organs with symptoms or warranting examination in the opinion of the Investigator or Subinvestigator. A symptom-directed physical exam will be performed only as needed, but may occur at any visit, predose, during infusions, and/or postdose (including for IRR). Clinically significant findings will be captured as an AE, followed by the Investigator, and managed appropriately per standard of care.

11.3.7 Electrocardiogram

A 10-lead or 12-lead ECG (without intensive QT analysis) will be obtained during screening after the subject has been in the supine position for ≥ 5 minutes and, if done on the same day as blood collection, before blood is drawn. The Investigator or qualified Subinvestigator will review

the ECG and assess any abnormalities for clinical significance. Any clinically significant findings will be captured as a baseline condition in the Medical History source document and eCRF. The ECG will be used to identify diseases or conditions that would put the subject at increased risk if participating in a clinical trial, so this should be considered when evaluating eligibility.

11.4 Clinical Laboratory Measurements

Blood and urine samples for clinical safety laboratory tests will be collected at the time points described below and in [Table 1](#). Investigators may have additional laboratory tests performed for the purpose of treatment planning or following AE or abnormal lab values. The site will process and ship blood and urine samples per central laboratory instructions. A central laboratory or designee will analyze blood and urine samples and provide results for the following clinical safety laboratory tests (Sections 11.4.1–11.4.10). For any laboratory test value outside the reference range that the Investigator considers clinically significant, the Investigator will:

- Repeat the test to verify the out-of-range value.
- Follow the out-of-range value to a satisfactory clinical resolution.
- Record as an AE, any laboratory test value after start of study drug that:
 - The Investigator considers clinically significant
 - Requires a subject to be discontinued from the study, or
 - Requires a subject to receive treatment.

Clinical laboratory testing will be performed centrally but may be performed locally due to issues associated with the coronavirus pandemic.

Testing for COVID-19 is not required for this study but may be implemented by the study site at any time during the clinical study due to safety regulations or procedures.

11.4.1 Complete Blood Count with Differential

Blood will be obtained for CBC with differential as described in [Section 11.2.8](#).

11.4.2 Blood Chemistry Profile

Blood will be obtained for chemistry tests during screening, predose on dosing days (Days 1, 29, 57, 85, 113, and 141), and on Days 169 and 197 (or ET). The blood sample will be processed and serum aliquots shipped per the central laboratory manual and laboratory kit instructions. The central laboratory will analyze the serum sample and provide results for chemistry tests including sodium, potassium, chloride, bicarbonate, glucose, blood urea nitrogen, creatinine, creatine

kinase, calcium, phosphorus, magnesium, total and direct bilirubin, total protein, albumin, alkaline phosphatase, alanine transaminase, aspartate transaminase, gamma-glutamyl transferase, and lactate dehydrogenase.

11.4.3 Urinalysis

Urine will be obtained for urinalysis during screening, as needed (if warranted in the opinion of the Investigator or Subinvestigator), and on Day 197 (or ET). The urine sample will be processed and shipped in accordance with the central laboratory manual and laboratory kit instructions. The central laboratory will analyze the urine sample for specific gravity, pH, protein, glucose, ketones, blood, and leukocyte esterase.

11.4.4 Serum Pregnancy and Follicle-Stimulating Hormone

Blood will be obtained from all female subjects of childbearing potential for a serum pregnancy test as measured by human chorionic gonadotropin (hCG). Females who are surgically sterile (tubal ligation, hysterectomy, or bilateral oophorectomy) for at least 3 months and females who are postmenopausal for at least 1 year with FSH level >30 mIU/mL are not considered to be of childbearing potential. To determine whether female subjects are post-menopausal or are of childbearing potential, blood for serum FSH will be obtained from all females during screening. The blood sample will be processed and shipped per the central laboratory manual and laboratory kit instructions. Both serum hCG and serum FSH will be analyzed by the central laboratory.

Females of childbearing potential (females with screening FSH level ≤ 30 mIU/mL) will provide a urine sample predose on dosing days (Days 1, 29, 57, 85, 113, and 141) for pregnancy (hCG) testing. The site will perform the urine pregnancy (hCG) test using an indicator stick from the kit supplied by the central laboratory. This test is to be assessed by the study staff, and study staff should confirm the subject is not pregnant prior to the start of each study drug infusion.

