Post-Dose Observation ²⁹		X			X	X	X	X	X			
Symptom-Directed Physical Exam ³⁰		X ¹		X ¹	X ¹	X ¹	X ¹	X ¹	X ¹	X ¹	X ¹	
Prior and Concomitant Medications	X	X	X	X	X	X	X	X	X	X ³⁴	X	
Adverse Events ³¹	X	X	X	X	X	X	X	X	X	X	X	X
Open-Label Extended Dosing ³⁴										X ³⁴	X ³⁴ – Day 197 visit does not apply to subjects in OLE period	

ADA: Anti-drug Antibody

ET: Early Termination

FSH: Follicle-Stimulating Hormone

IP: Investigational Product

CBC: Complete Blood Count

ECG: Electrocardiogram

hCG: Human Chorionic Gonadotropin

PK: Pharmacokinetics

DSQ: Dysphagia Symptom Questionnaire

EGD: Esophago-gastro-duodenoscopy

IRT: Interactive Response Technology

Table 1 Notes

- 1) Refer to assessment footnote for specific time points (e.g., predose, during infusion, postdose) to conduct the assessment on dosing days.
- 2) The screening period (Baseline) assessments can be conducted over multiple days within the screening period. The screening period must be a minimum of 14 days (2 weeks) and no longer than 60 days (or a maximum of 35 days after the Screening EGD, whichever is shorter). Day 1 can begin as soon as eligibility criteria are met.
- 3) Fecal collection kits for Ova and Parasite will be provided to subjects at the time of consent. Stool sample should be returned to the clinical site within 24 hours of collection.
- 4) At the time of consent, the Study Coordinator will activate all ePRO questionnaires in EDC, provide the subject with a unique username and password, train the subject on daily DSQ ePRO completion and compliance, and ensure the subject is able to complete the **CCI** questionnaire on their personal electronic device while on site.
- 5) Subjects should complete the DSQ daily after the last meal of the day. If Question 1 is answered “No,” the subject should answer the Solid Food Question ([Appendix 2](#)) after the DSQ is completed and submitted. The site is responsible for monitoring compliance throughout the duration of the study and discussing compliance during study visits.

Table 1 Notes cont.

- 6) On Day -2 (2 days before Day 1), on Day 15 (approximately 2 weeks after the first dose), and on Day 29 (approximately 4 weeks after the first dose), subjects will self-administer the CCI [REDACTED] after they submit the DSQ (and Solid Food Question, if applicable). On Day 15 and Day 29, subjects will also self-administer the CCI [REDACTED] after the DSQ, Solid Food Question (if applicable), and CCI [REDACTED].

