- 15) During the Screening EGD and Day 169 EGD, severity will be evaluated using the EoE Reference Score for Endoscopic Abnormalities per the study histology manual.
- 16) Please see the study central laboratory manual for collection, processing, and shipment instructions. If possible, samples should be shipped on the same day as collection.
- 17) Blood for serology (Hepatitis B surface antigen, Hepatitis C antibody, Hepatitis B core antibody, and HIV) will be obtained during screening.
- 18) For female subjects, blood will be obtained during screening to test for hCG (pregnancy) and FSH (post-menopausal status).
- 19) Blood for total serum IgE will be obtained on Days 1 (predose), 85 (predose), and 169 or ET, if subject early terminates before Day 169.
- 20) Blood for CBC with differential will be obtained at all study visits. On Days 1, 29, 57, 85, 113, and 141, blood will be drawn twice (predose and 1-hour postdose). For every CBC with differential blood collection except screening and Day 1 (predose), the blood count results will be blinded to the Sponsor and the site. The safety monitor may request an unscheduled CBC with differential. Blood counts from Day 197 will be used to determine if extended follow-up is needed.
- 21) Blood for chemistry will be obtained during screening, predose on dosing days (Days 1, 29, 57, 85, 113, 141), and on Days 169 and 197 (or ET).

Table 1 Notes cont.

- 22) Blood for PK will be obtained on Days 1, 8, 15, 29, 57, 85, 113, 141, 169, and 197 (or ET). Blood will be drawn predose on Days 1, 29, 57, 85, 113, and 141.
- 23) Blood for ADA will be obtained predose on Days 1, 29, 57, 85, 113, and 141, on Day 197 (or ET), and in the event of a suspected immunogenicity-related AE.
- 24) Blood for exploratory analysis will be obtained during screening and on Days 15, 169, and 197 (or ET).
- 25) If an infusion-related reaction results in infusion interruption or cessation, blood for exploratory safety analyses will be obtained within 1–2 hours of symptom onset.
- 26) Urine for standard urinalysis will be obtained during screening, as needed (if warranted in the opinion of the Investigator or Subinvestigator), and on Day 197 (or ET).
- 27) For females of childbearing potential, urine for dipstick pregnancy test will be collected, tested, and results confirmed predose on Days 1, 29, 57, 85, 113, and 141.

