7.3 Inclusion Criteria

Subjects with active EoE are eligible for enrollment into the study if all of the following criteria are met:

- 1) Male or female aged ≥ 12 and ≤ 80 years at the time of signing the ICF.
- 2) Confirmed diagnosis of EoE and intraepithelial eosinophilic infiltration of ≥ 15 eosinophils/hpf in 1 hpf from a biopsy collected during the Screening EGD without any other cause for the esophageal eosinophilia.
- 3) Baseline DSQ (biweekly mean DSQ) score of ≥ 12 from the last 2 weeks of screening (the 14 days prior to the first dose) per the validated algorithm in [Appendix 11](#).
- 4) History (by subject report) of an average of ≥ 2 episodes of dysphagia with intake of solid foods per week during the 4 weeks prior to screening.
- 5) Subjects must have failed or not be adequately controlled on standard of care treatments for EoE symptoms, which could include PPI, systemic or topical corticosteroids, and/or diet, among others.
- 6) If on an allowed treatment for EoE (per Section 8.2), stable dose for at least 4 weeks prior to screening and willingness to continue that dose for the study duration.
- 7) If subject is on preexisting dietary restrictions, willingness to maintain dietary restrictions throughout the study, as much as possible.
- 8) Able and willing to comply with all study procedures.
- 9) Female subjects must be either post-menopausal for at least 1 year with FSH level >30 mIU/mL at screening or surgically sterile (tubal ligation, hysterectomy, or bilateral oophorectomy) for at least 3 months, or if of childbearing potential, have a negative pregnancy test and either agree to use dual methods of contraception, have a partner who had a vasectomy, or agree to abstain from sexual activity from screening until the end of the study, or for 120 days following the last dose of study drug, whichever is longer.

Non-vasectomized male subjects with female partners of childbearing potential must agree to either abstain from sexual activity or agree to use a highly effective method of contraception from screening until the end of the study or for 120 days following the last dose of study drug, whichever is longer. All fertile men with female partners of childbearing potential should be instructed to contact the Investigator immediately if they suspect their partner might be pregnant at any time during study participation.

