12.2 The Day Before the First Infusion

- 1) Confirm eligibility.
- 2) Subject will self-administer oral prednisone premedication (dose based on body weight) 12–24 hours prior to the planned infusion start time. Ensure this is documented contemporaneously (e.g., subject emails the site when taking the premedication, subject texts the Study Coordinator when taking the premedication, etc.).

12.3 Day 1 – Dose 1

- 1) Pre-Infusion:
 - a) Confirm continued eligibility.
 - b) CCI to be self-administered by the subject via their personal electronic device.
 - c) Document any changes to health status.
 - d) Document any changes to concomitant medications including confirming and documenting the date and time the subject self-administered premedication.
 - e) Document any changes to baseline diet.
 - f) Determine body weight.
 - g) Collect vital signs.

- h) Perform symptom-directed physical exam, as needed.
 - i) Collect the following samples for the central laboratory:
 - Total Serum IgE
 - CBC with differential
 - Chemistry
 - Pharmacokinetics
 - Anti-drug antibodies
 - Urinalysis, if warranted in the opinion of the Investigator or Subinvestigator
 - j) Perform urine pregnancy test (if subject is of childbearing potential).
 - k) Enter the subject's PID and body weight in the IRT system to randomize the subject.
 - l) Once the subject has been randomized in the IRT system, the pharmacist will receive an email with PID, body weight, and kit number.
 - m) The study pharmacist will prepare study drug using the weight obtained at the visit. The final combined volume of the IV bag of study drug + 0.9% NaCl will be **120 mL**.

Note: **100 mL** of the calculated dose of study drug will be administered to the subject. The extra 20 mL is to be used to prime the IV infusion line during the preparation of the IV line at the bedside or to be left over in the infusion bag.
- 2) During the Infusion of Study Drug:
- a) Infuse 100 mL of study drug over at least 4 hours using an infusion pump per the instructions and infusion rate schedule in the Administration of Investigational Product section of the Pharmacy Manual. Record the start and stop times of the infusion including any times the infusion is interrupted.
 - b) Collect vital signs 15 (\pm 5) minutes after the start of infusion.
 - c) Perform symptom-directed physical exam, as needed.

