- 13) Blood for ADA will be obtained predose on Day 176 and on Day 372 (or ET). For Days 204, 232, 260, 288, and 316, blood for ADA will be obtained only if a suspected immunogenicity-related AE occurs.
- 14) Blood for exploratory analysis will be obtained predose on Day 316 and on Day 372 (or ET).
- 15) Blood for exploratory safety analyses will only be obtained within 1–2 hours of symptom onset if an IRR results in infusion interruption or cessation.
- 16) Urine for urinalysis will be obtained predose on Day 176, as needed (if warranted in the opinion of the Investigator or Subinvestigator), and on Day 372.
- 17) For females of childbearing potential, urine will be collected, tested, and pregnancy result confirmed predose on Days 176, 204, 232, 260, 288, and 316.

Table 5 Notes cont.

- 18) The day before the first open-label AK002 dose (12–24 hours prior to the infusion start time), subjects will self-administer oral prednisone premedication at a dose of 40 mg if body weight is <40 kg, 60 mg if body weight is \geq 40 kg and <60 kg, or 80 mg if body weight is \geq 60 kg. This dose of prednisone premedication should be recorded in the Concomitant Medications CRF of both the AK002-014 treatment period database and the AK002-014 OLE period database.
- 19) Open-label AK002 will be administered as a single peripheral IV infusion over \geq 4 hours on Day 176, over \geq 3 hours on Day 204, and over \geq 2 hours on Days 232, 260, 288, and 316. Refer to the Pharmacy Manual for detailed administration and infusion rate schedule instructions.
- 20) Subjects will remain under observation at the site for at least 1 hour after the end of each infusion. In the event of an IRR, the subject may require prolonged observation (>1 hour or until the symptoms resolve), as per Investigator discretion. Subjects will also be instructed to immediately contact the study doctor if any reactions occur after discharge.
- 21) If a new or worsening symptom (or clinically significant finding) is observed or reported, the Investigator or designee will determine whether a symptom-directed physical examination is warranted. Symptom-directed physical examinations will be performed if warranted (per the Investigator or designee judgment) and may be performed at any time or multiple times during a visit (predose, during infusion, and/or postdose).

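### Section 11.4.4 defines the predose pregnancy-test group by FSH alone, which leaves out some women whom Inclusion Criterion 9 treats as able to conceive

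*Protocol*

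**What the plan says.** Three kinds of protocol text decide who is tested for pregnancy before dosing.

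- **The definition.** Inclusion Criterion 9 (Section 7.3) gives two ways for a woman to fall outside childbearing potential: "Female subjects must be either post-menopausal for at least 1 year with FSH level >30 mIU/mL at screening or surgically sterile", with sterility lasting at least 3 months. The first paragraph of Section 11.4.4 agrees. It accepts surgical sterility of at least 3 months, and adds that "females who are postmenopausal for at least 1 year with FSH level >30 mIU/mL are not considered to be of childbearing potential".
- **The test procedure.** The second paragraph of Section 11.4.4 reads: "Females of childbearing potential (females with screening FSH level ≤ 30 mIU/mL) will provide a urine sample predose on dosing days". It ends by asking staff to confirm before each infusion that the subject is not pregnant.
- **The schedule and checklists.** Table 1 note 27 (Section 5.2), which covers all six dosing days, reads: "For females of childbearing potential, urine for dipstick pregnancy test will be collected, tested, and results confirmed predose". The six dosing-visit checklists (Sections 12.3 and 12.6 to 12.10) likewise condition the test on childbearing potential. None of these texts sets an FSH limit or defines the term.

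For the open-label period, Table 5 note 17 also uses the term without an FSH limit: "For females of childbearing potential, urine will be collected, tested, and pregnancy result confirmed predose".

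**The concern.** The definition joins two conditions for a non-sterile woman: time since menopause and FSH. The parenthesis keeps only FSH and drops both the 1-year condition and sterility. It stands in the sentence that describes how the predose test is run, where a coordinator unsure of the term is likely to look.

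The first paragraph of Section 11.4.4 may reinforce an FSH-only reading, because it presents the screening FSH sample as the means of sorting women into post-menopausal and childbearing groups. FSH is scheduled only at screening (Table 1 note 18), so a woman misclassified then would stay misclassified through Day 141.

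The predose dipstick is the only pregnancy test that Table 1 schedules after screening. Pregnancy is an exclusion (Exclusion Criterion 20), and Section 13.7.3 requires study drug to stop at once if it occurs. What is at stake is repeat testing before infusions in women the protocol itself regards as able to conceive. No endpoint, power or type I error element is involved.

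**Working it through.** The plan gives no figure to reproduce. The check is logical, with one short date calculation.

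**Inputs**

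- Definition A (Inclusion Criterion 9 and Section 11.4.4, first paragraph): childbearing potential = not sterile AND NOT (at least 1 year post-menopausal AND FSH > 30).
- Definition B (parenthesis in Section 11.4.4, second paragraph): childbearing potential = FSH ≤ 30.
- Three yes/no attributes: surgically sterile for at least 3 months, FSH > 30, at least 1 year post-menopausal. That gives 2 × 2 × 2 = 8 profiles. The under-1-year rows include women who have not reached menopause.

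| Sterile | FSH (mIU/mL) | Post-menopausal | A | B | Result |
|---|---|---|---|---|---|
| No | > 30 | ≥ 1 year | No | No | Agree |
| No | > 30 | < 1 year | **Yes** | **No** | **Test missed** |
| No | ≤ 30 | ≥ 1 year | Yes | Yes | Agree |
| No | ≤ 30 | < 1 year | Yes | Yes | Agree |
| Yes | > 30 | ≥ 1 year | No | No | Agree |
| Yes | > 30 | < 1 year | No | No | Agree |
| Yes | ≤ 30 | ≥ 1 year | No | Yes | Needless test |
| Yes | ≤ 30 | < 1 year | No | Yes | Needless test |

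Five profiles agree and three disagree: one missed, two tested needlessly. If the parenthesis is read as an extra condition on top of A, rather than as a replacement for it, the two needless rows disappear. The missed row remains under either reading.

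**Tests lost.** The predose tests fall on Days 1, 29, 57, 85, 113 and 141, so up to 6 would be skipped for the missed profile.

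**Time since her last scheduled test.** Assume the screening hCG is drawn at the start of screening and ignore visit windows. Table 1 note 2 states: "The screening period must be a minimum of 14 days (2 weeks) and no longer than 60 days".

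- Day 1 to Day 141: 141 − 1 = 140 days.
- Shortest screening: 14 + 140 = 154 days before the last infusion.
- Longest screening: 60 + 140 = 200 days before the last infusion.

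Note 2 also caps screening at 35 days after the Screening EGD. A 60-day screening therefore needs the EGD no earlier than 60 − 35 = 25 days into it, so 200 days is an extreme. Drawing the hCG later in screening shortens both figures.

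**After the fix.** With the parenthesis removed, A applies everywhere and all 8 profiles agree.

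**The case against.** The strongest reply is that the sentence is about females of childbearing potential, and the paragraph directly above defines that term correctly. To skip the test, a site must let a parenthesis override that definition, Inclusion Criterion 9, Table 1 note 27 and six checklists. The checklists and note 27 are what staff follow visit by visit. This stands as a limit on how likely the error is. It does not remove the conflict: note 27 and the checklists leave the term undefined, and a site that takes its definition from the test procedure could believe it was complying.

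Other protections also remain. Screening serum hCG covers female subjects. Inclusion Criterion 9 requires a negative pregnancy test together with dual contraception, a vasectomised partner or abstinence. Eligibility is reconfirmed before each infusion, and a woman who becomes pregnant must stop study drug and report it. All of this is true, so what is lost is one layer of protection. None of these measures replaces a scheduled test after screening.

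The counts of 1 in 8 and 2 in 8 are cells in a logical table and say nothing about how many women are affected. That is correct, and they should not be read as risks.

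Finally, an amendment is not free. Section 17.1 requires health-authority submission, prior IRB approval and investigator signature, and the synopsis foresees up to about 90 centres. This is a fair point about timing. It argues for making the correction alongside other changes, not for leaving the text as it is.

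**Conclusion.** The concern holds. The FSH-only parenthesis in Section 11.4.4 contradicts that section's first paragraph and Inclusion Criterion 9, and for the group that matters it is narrower than Table 1 note 27 and the six checklists. Nothing in the documents justifies an FSH-only testing group, so it reads as loose shorthand and not as a deliberate choice.

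The consequence depends on a site applying the parenthesis. A non-sterile woman with FSH above 30 who is under 1 year post-menopausal would then miss up to 6 predose tests. Her last scheduled test would precede the Day 141 infusion by 154 to 200 days, if the hCG was drawn at the start of screening. At a site using the first-paragraph definition, no test is missed. The number of such women is not given and is probably small. No claim is made about the open-label period. The wording should be corrected because it governs a safety procedure, but it has no bearing on the efficacy analysis.

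**What to change.** In the second paragraph of Section 11.4.4, delete the parenthesis that gives the FSH limit, or replace it with *as defined above and in Inclusion Criterion 9*. One definition then governs contraception, serum hCG, Table 1 note 27, the six dosing-visit checklists and Table 5 note 17.

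The change is one phrase and can go into the next amendment made for other reasons. A few more dipsticks would be used from kits the central laboratory already supplies, offset by fewer in surgically sterile women.
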